 - (4) Change in subject specific memory, defined as the MSVT, between baseline and six months post-conversion in both arms
 - (5) Change in subject specific cognitive function, defined as the MoCA, between baseline and six months post-conversion in both arms
 - **(6)** Change in subject specific renal function, defined as the 4 variable MDRD, between baseline and six months post-conversion in both arms

5) Inclusion & Exclusion Criteria

- i) Potentially eligible patients will be screened by the PI and study coordinator using inclusion and exclusion criteria below to determine if they qualify for the study.
- ii) Inclusion criteria
 - (1) Male or female adult (≥18 years old) with a history of liver or liver/kidney transplant within 15 days to 12 months of transplant.
 - (2) Patients must be capable of understanding the purposes and risks of the study and have the ability to give written informed consent and be willing to participate and comply with the study. For those that consent virtually, subjects must be willing and able to use the Doxy.me platform and complete assessments virtually.
- iii) Exclusion criteria
 - (1) Patients will be excluded if they are pregnant or nursing females or males with a pregnant female partner
 - (2) HIV positive (HIV ab +)
 - (3) Unable to tolerate oral medications
 - (4) Use of another investigational product within thirty days prior to receiving study medication
 - (5) Moderate acute cellular rejection (RAI ≥ 5) within the past month
 - **(6)** A condition that is known to cause tremor such as essential tremor, Parkinson disease, or enhanced physiologic tremor.
 - (7) Patients taking medications known to induce tremors or dopamine blocking agents

(8) A condition or disorder that, in the opinion of the investigator, may adversely affect the outcome of the study or the safety of the subject

6) Number of Subjects

a) There will be 15 subjects in each arm, 30 subjects total

7) Setting Where Research Will Be Conducted

a) Study activities, including consent, enrollment, and randomization, will occur in the Liver Transplant Clinic at the Medical University of South Carolina or through Doxy.me.

8) Recruitment Methods

- a) Study enrollment procedures

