 - (1) Opportunistic infections will be defined as outlined in Appendix F
- v) Intervention Discontinuation Evaluations: At the scheduled time of intervention discontinuation (EOT, last date of study), the following evaluations must be completed: clinical assessment, CBC, CHEM-7, LFTs, Tacrolimus CO. In case of subject withdrawal from study, the patient will return to standard of care medications and request to continue with final assessment using PGI-I, IMAB-Q 10, MSVT, MoCA, SF-12, MMSE, and FTM (if applicable) will be discussed with a qualified team member.

12) Data Management

- a) Data management will be overseen and data analysis will be independently reviewed by an Investigator on the study who has no related financial interest. This member will serve as independent monitor to oversee data collection and management, and to verify the integrity of data and interpretation of study results. Data reports, including patient recruitment and randomization numbers, clinical outcomes (acute rejections, infections and hospitalizations), AEs and SAEs will be reviewed quarterly.
- b) Dichotomous data will be analyzed using Chi Square or Fischer Exact, when appropriate, and continuous data points will be analyzed using Student's t-test or Mann Whitney U, for parametric and nonparametric data, respectively.
- c) Sample size estimation for the primary outcome
 - i) The proposed sample size (n=30) would be able to demonstrate a mean difference in neurologic toxicity burden, using the Patient Global Impression of Improvement (PGI-I) rating of 20 ± 15 with greater than 80% power using a two-tailed t-test with an alpha set at 0.05. Based on reported neurologic toxicities from the literature (headache 64%, insomnia 64%, tremor 56%, paresthesia 40%), a mean score of 45 is expected at baseline. Using the independent samples t-test comparing two groups with a two-sided significance level of

0.05, a sample size of 14 subjects per group would be required to obtain a power of at least 0.8 if the two groups have a mean of 25 ± 15 neurologic toxicity burden in the Envarsus cohort at the conclusion of the study and mean of 45 ± 20 neurologic toxicity burden at baseline and follow up in the tacrolimus IR group. Estimating a 10% drop out rate, we propose a sample size of 15 subjects per group. This sample size will provide adequate power to show a statistical and clinical difference in the neurologic toxicity burden between the two groups.

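### Section 12(c): a 10% drop-out allowance on 14 per group rounds up to 16, not 15; the effect on power is small, but the statement should be corrected

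*Combined protocol and SAP*

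**What the plan says.** Section 12(c) of the combined protocol and SAP sizes the trial on the composite PGI-I score, compared between arms by a t-test at a two-sided 0.05 level. It describes the assumptions twice.

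- The opening sentence gives a mean difference as a "rating of 20 ± 15 with greater than 80% power using a two-tailed t-test", for the full 30 subjects.
- The detailed calculation assumes a "mean of 25 ± 15 neurologic toxicity burden in the Envarsus cohort at the conclusion of the study" and a "mean of 45 ± 20 neurologic toxicity burden at baseline and follow up in the tacrolimus IR group". On that basis, "a sample size of 14 subjects per group would be required to obtain a power of at least 0.8".

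The drop-out step follows: "Estimating a 10% drop out rate, we propose a sample size of 15 subjects per group". No inflation formula is shown. Section 6 repeats the result: "There will be 15 subjects in each arm, 30 subjects total". Section 10 allocates these 30 in three permuted blocks of ten.

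Two other places bear on what a drop-out costs. Section 12(d) includes all subjects under intention-to-treat, expects some missing data and names no imputation method. Section 11(v) says that a final assessment, including PGI-I, will be discussed with subjects who withdraw.

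**The concern.** An allowance for drop-out is meant to leave the required number of evaluable subjects after the expected loss. Here the plan names the required number (14), the loss (10%) and the enrolment (15), and the three do not fit together: nine tenths of 15 is less than 14. A reader who takes the paragraph at its word will believe that a 10% loss has been covered, when only one loss per arm has been. If the shortfall were large, the trial would be under-powered for its primary outcome at its own expected drop-out. The paragraph also carries two sets of standard deviations, so the reader cannot tell which power figure the trial relies on.

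**Working it through.** **Inputs, all from section 12(c).** Two-sided alpha 0.05; difference 45 − 25 = 20; SDs 15 (Envarsus) and 20 (tacrolimus IR); 14 evaluable per group; 10% drop-out; 15 enrolled per group.

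**1. Reproduce the 14.** Common SD for equal groups: √((15² + 20²)/2) = √312.5 = 17.68. Standard error: 17.68 × √(1/n₁ + 1/n₂). Non-centrality: 20 divided by the standard error. Power comes from the noncentral t distribution with n₁ + n₂ − 2 degrees of freedom.

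- 13 per group: standard error 6.93, non-centrality 2.88, power 0.790.
- 14 per group: standard error 6.68, non-centrality 2.99, power 0.822.

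The smallest number giving at least 0.80 is 14, as the plan says. The Welch (unequal-variance) version gives 0.788 and 0.819, hence the same answer.

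**2. Apply the drop-out allowance.**

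- Dividing by the retained fraction: 14/(1 − 0.10) = 15.56, so 16 per group (32 in total).
- The cruder rule: 14 × 1.10 = 15.4, which also rounds up to 16.
- The plan's 15: 15 × 0.90 = 13.5 expected completers per group, or 27 of 30.
- Loss that 15 can absorb while keeping 14: 1/15 = 6.7%.

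**3. Power that 15 per group delivers (SDs 15 and 20).**

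| Completers | t-test power, common SD | Welch |
|---|---|---|
| 15 + 15 (no drop-out) | 0.849 | 0.847 |
| 14 + 14 (one loss per group) | 0.822 | 0.819 |
| 13 + 14 (27 in total) | 0.806 | 0.798 or 0.809, depending on which arm loses more |
| 13 + 13 | 0.790 | 0.788 |
| Average over random 10% drop-out from 15 per arm | 0.803 | 0.800 |

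For comparison, 16 + 16 with no loss gives 0.872.

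**4. The other SD statement.** Read 20 ± 15 as a difference of 20 with SD 15 in each arm. The plan does not spell this out, so the reading is an assumption. Power is then 0.941 at 15 + 15, 0.914 at 13 + 14 and 0.903 at 13 + 13. On these inputs 9 per group gives 0.757 and 10 gives 0.805, so the requirement would be 10 per group. Of the paragraph's two sets, only SDs of 15 and 20 lead to 14.

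**The case against.** The strongest reply is that no power figure in the paragraph is shown to be false. Fourteen per group does give at least 0.80. Thirty subjects do give more than 0.80 for 20 ± 15, even after a 10% loss. The plan never says that 14 completers will remain, only that 15 per group is adequate, and expected power after drop-out is still about 0.80. This stands, and it limits the point to the rounding of the allowance.

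It can also be said that a drop-out is not necessarily a lost outcome, since withdrawn subjects may be asked for a final PGI-I and the analysis is by intention-to-treat. This stands in part. The assessment is only to be discussed with the subject and no imputation method is given. The plan's own allowance treats drop-outs as subjects to be replaced in the count. Treating every drop-out as lost is the cautious case.

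Three stronger readings are tempting, and the documents do not support them.

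- *The trial is under-powered at its stated drop-out.* On the 15 and 20 inputs the average is 0.80. On the 20 ± 15 statement power stays above 0.90, so the lack of reserve belongs to the first set only.
- *At least one arm will probably fall below 14, so the design fails.* With independent 10% losses that chance is about 70%, but it says little about power. Fourteen is a rounded-up number carrying 0.82, and 13 + 14 still gives 0.81.
- *The Mann-Whitney alternative falls below 80%.* Section 12(b) reserves that test for nonparametric data. A power figure for it computed on normal data describes a case in which the plan would use the t-test. The documents give no distribution from which a relevant figure could be derived.

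**Conclusion.** The allowance is mis-rounded by one subject per group: 16 is needed to retain 14 at 10% drop-out, and 15 covers a loss of 6.7%. The cost in power is about two percentage points against the plan's 14 completers (0.822 to about 0.80). The 80% target is thus met on average with nothing in reserve, and is missed by one point at 13 per group. These figures rest on the plan's means, SDs of 15 and 20, normally distributed scores, the same 10% loss in both arms, and drop-outs contributing no primary outcome. This is a minor correction, and it does not show that the trial is too small. The two SD statements remain unreconciled. The documents do not settle which should govern, although only the 15 and 20 pair yields the stated 14.

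**What to change.** Amend section 12(c) and leave enrolment at 15 per group.

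1. Replace the drop-out sentence with one of two accurate statements. Either 15 per group allows for one loss per group (6.7%) while keeping 14 evaluable; or, with 10% drop-out and about 27 completers, t-test power is about 0.80 for 25 ± 15 against 45 ± 20.
2. Reconcile the opening 20 ± 15 with the SDs of 15 and 20 used later. The sponsor should say which set the sample size rests on, noting that 14 per group follows only from the latter.

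The cost is wording only. Sections 6 and 10, including the three blocks of ten, stay as they are. The stated power after drop-out becomes slightly less favourable than the paragraph now suggests.

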Neurotoxicity associated with tacrolimus after liver transplant has been reported in 10 to 42% of recipients (1-7). These toxicities can range from mild (tremors, headaches) to severe (seizures, PRES memory loss) and are a significant cause of morbidity after liver transplantation. Neurotoxicities are the most frequent adverse events that lead to tacrolimus discontinuation in abdominal transplant recipients, which leads to an increased risk of acute rejection, including 31% in liver transplant recipients in the first year after conversion (8).

Although the vast majority of literature in liver transplant neurotoxicities focus on the acute, severe neurotoxicities (PRES, seizures), there is evidence that more mild neurotoxicities can persist and lead to significantly worse visuospatial/constructional ability, impaired cognitive function, and white brain matter changes (9).

In several chronic disease states, adverse drug events have clearly been established as a major risk factor for medication non-adherence (10-12). Additionally, adverse drug events are associated with significant healthcare utilization and costs (13,14).

Tacrolimus LCP (Envarsus®) is a once-daily tacrolimus product that has demonstrated an ability to maintain a similar Cmin to tacrolimus IR in converted liver transplant recipients with an average

conversion dosing ratio of 0.7, while also demonstrating significantly less variability in levels. In an extension study of this group, the pharmacokinetics of tacrolimus LCP remained stable up to 26 weeks post-conversion and there were no concerns for safety at up to 52 weeks on tacrolimus LCP (15). Tacrolimus LCP has also demonstrated a significant improvement in tremor compared to tacrolimus IR in kidney transplant recipients experiencing a clinically significant tremor (16). Hand tremors exist with a high incidence in liver transplant recipients, worsening after administration of cyclosporine or tacrolimus (16), and can be a major contributor to reduced quality of life. We hypothesize that tacrolimus LCP will show a lower neurotoxicity burden in multiple neurologic side effects, as compared to tacrolimus IR.

Supporting Data

Multicenter Open-label Conversion Trial for Abdominal Transplants Unable to Tolerate Tacrolimus

Overall Distribution of ADRs Prompting Conversion from Tacrolimus						
Kidney (n=49) Liver (n=108						
Neurotoxicity	20 (41)	67 (62)				
Gastrointestinal	9 (18)	29 (27)				
Nephrotoxicity	4 (8)	20 (19)				

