- d) Missing data and imputation methods
 - i) Under the intention-to-treat principle, all subjects are included in the analysis. Extensive efforts will be made to keep all missing data to a minimum and minimize loss to follow-up (LTFU). However, it is likely that some missing data may occur.
- e) Data Handling and Record Keeping
 - i) In order to protect subjects against any risk regarding loss of personal information, all obligations under the Health Portability and Accountability Act (HIPPA) will be met. Additionally, all data will be collected and stored through the secure network server and behind the MUSC firewall. We will use electronic CRF forms to gather all study information (redcap.musc.edu). Data will only be stored on campus computers under the MUSC secure network. Data collection forms will be maintained within an office, which is a locked office facility on campus. Only approved study members will have access to patient data.
 - ii) Any data or information shared for dissemination will be de-identified and the confidentiality of all participants will be strictly maintained. The only persons with access to protected health information (PHI) will include study investigators, research coordinators and those approved by the MUSC IRB. All data will be secured on MUSC servers, behind firewalls, with passwords protecting entry in these systems. All PHI will be obtained and managed in accordance with the HIPAA Privacy Rule (45 CFR Parts 160 and 164).

13) Provisions to Monitor Data and Ensure Subject Safety

- a) Study modification/discontinuation
 - (1) The study may be modified or discontinued at any time by the IRB, the sponsor, the OHRP, the FDA, or other government agencies as part of their duties to ensure that research subjects are protected.
 - (2) After 16 subjects have been randomized and completed follow-up, efficacy and safety endpoints will be reviewed by a blinded Safety Monitor to identify if the risk profile is as expected. If significantly increased risk is identified in either or both arms of the study, sufficient to increase the risk over the potential benefit of the study, the study will be discontinued. Examples are included below:
 - (a) A 6-month rejection rate difference between arms > 20%
 - **(b)** A difference in grade 3 or higher infections (based on CTCAE) between arms of > 20%
 - (c) A graft loss difference between arms > 20%

b) Adverse Events

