 - i) AEs and SAEs will be reported in accordance with the FDA Guidelines for Post-Marketing Reporting of Adverse Events 21 CRF 314.80 and 21 CRF 600.80 http://www.fda.gov/medwatch/report/regs.htm. Any serious adverse event or a non-serious adverse event that is related to the study and unexpected will be reported to the FDA, per reporting guidelines, as soon as possible, but no later than 15 working days. Further, all serious adverse events that are related to the study and are unexpected must be reported to The Medical University of South Carolina IRB within 10 days per The Medical University of South Carolina IRB Unanticipated Problems and Adverse Events Policy and Procedures reporting guidelines.

14) Withdrawal of Subjects

- a) Criteria for intervention discontinuation
 - (1) The intervention will be withheld/discontinued for AE of grade 3 or higher or if requested by the study participant.
 - (2) Additionally, the intervention will be discontinued if the subject meets criteria for the following reasons:
 - (a) Loss of graft: Defined as death or need for retransplant. Patients will be deemed a treatment failure and the intervention will be discontinued.

15) Risks to Subjects

- a) An increased risk of getting some kinds of cancer, including skin and lymph gland cancer (lymphoma)
- b) An increased risk of infections. As immediate release tacrolimus can lower the ability of the immune system to fight infections, serious infections can happen in people taking immediate

release tacrolimus that can cause death. Patients should call their doctor right away if they have symptoms of an infection such as fever; sweats or chills; cough or flu-like symptoms; muscle aches; or warm, red, or painful areas on their skin

- c) High blood sugar (diabetes)
- d) Kidney injury and decreased kidney function
- e) Nervous system problems including encephalopathy, delirium, seizures, coma, tremors, paresthesia, headache, mental status changes, and changes in motor and sensory functions
- f) High levels of potassium in the blood (potassium is important for nerve and muscle function)
- g) High blood pressure
- h) Heart problems (myocardial hypertrophy)
- i) The most common side effects for Envarsus® Daily and Tacrolimus IR in people receiving kidney transplant are

En	ıvarsus XR	Tacrolimus IR	
Infection	70%	65%	
Tremors	19%	17%	
High Blood Pressure	23%	23%	
Kidney Problems	10%	10%	
Constipation	18%	25%	
Diarrhea	31%	34%	
Headache	15%	10%	
Trouble Sleeping	13%	11%	

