Appendix A: Scientific Registry of Transplant Recipients

Program Summary: MUSC

Medical University of South Carolina

Center Code: SCMU

Transplant Program (Organ): Liver Release Date: January 5, 2018

Based on Data Available: October 31, 2017

SRTR Program-Specific Report Feedback?: [contact] [name] http://www.srtr.org

A. Program Summary

Figure A1. Waiting list and transplant activity

[figure not shown]

Table A1. Census of transplant recipients

Recipients	07/01/2015- 06/30/2016	07/01/2016- 06/30/2017
Transplanted at this center	69	93
Followed by this center*	658	658
transplanted at this progran	n 620	614
transplanted elsewhere	38	44

^{*} Recipients followed are transplant recipients for whom the center has submitted a post-transplant follow-up form for a transplant that took place before the 12-month interval for each column.

Figure A2. Transplant rates 07/01/2015 - 06/30/2017

[figure not shown]

Figure A3. Waiting list mortality rates 07/01/2015 - 06/30/2017

Figure A4. First-year adult graft and patient survival: 07/01/2014 - 12/31/2016

[figure not shown]
[figure not shown]

Figure A5. First-year pediatric graft and patient survival: 07/01/2014 - 12/31/2016

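### Does the 16-subject safety review need stated expected event rates, given that its three examples are all differences between arms?

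*Combined protocol and SAP*

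**What the plan says.** Section 13a)(2) sets one formal review, after 16 subjects have been randomized and have completed follow-up. Efficacy and safety endpoints are "reviewed by a blinded Safety Monitor to identify if the risk profile is as expected". The action follows in the next sentence: "If significantly increased risk is identified in either or both arms of the study", and that risk is enough to outweigh the study's potential benefit, the study is discontinued. Three criteria are then listed, expressly as examples:

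- "A 6-month rejection rate difference between arms > 20" per cent;
- "A difference in grade 3 or higher infections (based on CTCAE) between arms of > 20" per cent;
- "A graft loss difference between arms > 20" per cent.

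The section names no expected rate, historical comparator or pooled count. Section 12a) adds a quarterly review of acute rejections, infections, hospitalizations, AEs and SAEs, without thresholds. Section 13a)(1) lets the IRB, the sponsor or the regulators modify or stop the study at any time.

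**The concern.** The section asks whether risk is as expected but does not say what is expected. It then names a rise in both arms as a ground for stopping, yet every example is a contrast between arms. A contrast carries no information about a level that the arms share. If both arms did badly to the same degree, the difference would stay near zero and no example would be met.

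The rest of the protocol does not supply the missing reference.

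- **Rejection.** The only rate is in the Rationale (section 2a), for patients taken off tacrolimus: "which leads to an increased risk of acute rejection, including 31% in liver transplant recipients in the first year after conversion". Neither arm is that population.
- **Infection.** The only rates, 70% and 65% in section 15i), come from kidney recipients and are not restricted to grade 3 or higher.
- **Graft loss.** Appendix A lists a figure titled "First-year adult graft and patient survival: 07/01/2014 - 12/31/2016". It may help, but 13a) does not point to it, and its content cannot be seen in the text available here.

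At stake would be a safety review that two careful monitors could read differently, in the only review that has numerical criteria.

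**Working it through.** The plan gives no figure on this point to reproduce. The inputs are 16 subjects and a 20-point difference (13a)(2)) and 1:1 allocation in blocks of ten (10b). An 8 v 8 split is assumed unless stated. All event rates below are assumptions, because the documents give none that fit.

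**1. What the examples can show.** With 8 per arm, a gap of one event is 1/8 = 12.5 points and a gap of two is 2/8 = 25 points, so an example needs a gap of at least two events. Given m events in all and no arm effect, the chance that an example is *not* met is:

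- m = 5: 2·C(8,3)·C(8,2)/C(16,5) = 3136/4368 = 0.718
- m = 6: C(8,3)²/C(16,6) = 3136/8008 = 0.392
- m = 7: 2·C(8,4)·C(8,3)/C(16,7) = 7840/11440 = 0.685
- m = 8: C(8,4)²/C(16,8) = 4900/12870 = 0.381

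Averaged over the 8:8, 9:7 and 10:6 splits that blocks of ten allow for the first 16 allocations, these become 53% to 55%. So a high shared count often meets no example, and when it does meet one the cause is chance imbalance.

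**2. One example at a common true rate p.** The exact binomial P(|difference| > 0.20) is 7.9% at p = 5%, 19.2% at 10%, 33.9% at 20%, 41.1% at 30% and about 45% at 50%, its maximum. That ceiling applies to one endpoint. For any of three independent endpoints at 10/20/5%, the chance is 1 − 0.808 × 0.661 × 0.921 = 50.8%.

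**3. What a pooled count would add.** The illustrative counts are 5 or more rejections, 7 or more infections and 3 or more graft losses in 16.

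| Endpoint | Common rate | Pooled count met | Example met |
|---|---|---|---|
| Rejection | 10% | 1.7% | 19% |
| Rejection | 20% (doubled) | 20% | 34% |
| Rejection | 30% (tripled) | 55% | 41% |
| Infection | 20% | 2.7% | 34% |
| Infection | 40% (doubled) | 47% | 44% |
| Graft loss | 5% | 4.3% | 8% |
| Graft loss | 10% (doubled) | 21% | 19% |
| Graft loss | 15% (tripled) | 44% | 28% |

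The pooled count overtakes the example clearly only when rejection or graft loss triples. When rates double, it is met less often for rejection and about as often for the other two. It does raise far fewer chance flags: any of the three is met 8.4% of the time at 10/20/5%, against 50.8% for the examples.

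**4. Price and gain of adding it.** At 10/20/5% the chance of any flag goes from about 51% to 54%. With all three rates doubled it goes from 70.3% to 89.8%. If the true background is 15/30/5% and the counts stay at 5, 7 and 3, any flag goes from about 61% to 71% with no rise at all. The price therefore turns on rates that someone would still have to choose.

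**5. The text itself.** The operative sentence names both arms and sets a risk-benefit test. The list after it is declared to be examples. Nothing tells the monitor to stop only if an example is met, or to ignore the total.

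**The case for a change.** The strongest case for a change is that a judgement about what is expected needs an expectation. Five or more rejections in 16 has probability 1.7% if 10% is expected and 58% if 31% is taken, so the same data can read as an alarm or as ordinary. Stating the rates would take a paragraph, remove no example and need no arm identity, which suits a blinded monitor.

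Part of this stands: the section is silent on rates, and none of its examples illustrates the both-arms limb. The 31% end of the contrast does not stand. It is a first-year rate after leaving tacrolimus, so no monitor should adopt it for either arm.

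The supposed mechanism is also thin. Section 3a) defines the control arm as standard of care, and it describes both products as used that way for all organ transplants. Interim laboratory tests are collected only if done in routine care (section 10f), biopsies are done when clinically warranted, and rejection is treated at the provider's discretion (section 11). Little that the arms share is imposed by the trial, so a parallel rise would mostly reflect background risk, which a concurrent randomized control is there to reveal. A cluster of events would also come up in the quarterly review under 12a), and 13a)(1) allows action on it at any time.

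**Conclusion.** No change follows. The facts are as described: no expected rates, and three examples that cannot register a similar rise in both arms. But the rule that governs stopping already covers such a rise by judgement, and the examples do not limit it. No stated rule therefore produces a wrong decision. What is missing is reference detail that a monitor can reasonably supply from experience of the population, by looking at the total as well as the gap. Writing it down would leave the rates, the counts and their consequence still to be chosen, and a separate monitoring document would serve as well.

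The size of any benefit is uncertain. It ranges from none for a doubling of rejection (pooled count 20%, example 34%) to a moderate gain for a tripling (55% against 41%). The added chance flags range from about 3 to 10 percentage points over the two sets of background rates tried. All these figures rest on assumed rates, an 8 v 8 split and, for the any-flag values, independent endpoints. The conclusion itself rests on the wording of 13a)(2) and on the monitor receiving event counts for each arm, even if the arms are masked.
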